## 6.1 Other Risks Associated with Drugs of the Same Class

MAAA-1181a is a derivative of exatecan (DX-8951f), a topoisomerase I inhibitor. Other products of the same class include irinotecan ([Irinotecan package inserts. 2016](#)) and topotecan ([Topotecan package inserts. 2015](#)). Exatecan is a camptothecin derivative, which has previously been developed by the former Daiichi Pharmaceuticals Co., Ltd. as an anti-cancer therapy.

The main risks associated with the use of topoisomerase I inhibitors include hematological toxicities and gastrointestinal toxicities. Hematological toxicities, manifesting as neutropenia, febrile neutropenia, anemia, thrombocytopenia, and pancytopenia are commonly observed. An increased risk of infections, including neutropenic colitis, neutropenic sepsis, and disseminated intravascular coagulopathy has been reported with these agents.

Diarrhea and delayed onset diarrhea, which can be severe and lead to dehydration, have been associated with topoisomerase I inhibitors. Other gastrointestinal toxicities include nausea, vomiting, ileus, and intestinal perforation. Acute cholinergic syndrome, manifesting as diarrhea and other cholinergic symptoms have been reported with irinotecan. Other significant risks include ILD, liver impairment, renal impairment, anaphylaxis, myocardial ischemic events, and thromboembolic events.

The safety profile of exatecan is broadly similar to the safety profile of other topoisomerase I inhibitors, with hematological toxicities and gastrointestinal toxicities being the most significant groups of events ([Cheverton et al. 2004](#), [Deciphera 2019](#), [De Jager et al. 2000](#)).

## 7. STUDY ASSESSMENTS AND EVALUATIONS

### 7.1 Overview

All patients should visit the study center on the days specified within this protocol. The complete Schedule of Assessments for this study is presented at the beginning of this protocol (see [Assessment Schedule](#)). The key procedures required in this study include:

- All AEs regardless of seriousness or relationship to DS-6157a treatment (called study treatment) spanning from the signing of the ICF until at least 30 calendar days after the patient's last dose of study drug, or the patient's start of another cancer treatment are to be recorded on the corresponding screen(s) included in the eCRF.
- PK samples throughout the study
- Baseline and on-treatment blood biomarker and immunogenicity assessments
- Tumor biopsy biomarker assessments
- Tumor assessments (based on computed tomography [CT]/positron emission tomography [PET]/ and/or magnetic resonance imaging [MRI] scan) according to RECIST Version 1.1 ([Appendix B](#)).

A cycle of treatment is scheduled to last 3 weeks (21 calendar days). Multiple procedures may be scheduled at the same time point relative to DS-6157a dosing. Priority must be given to PK collection at the time specified. Vital signs and ECG assessments must be performed prior to PK sample collections when these assessments are scheduled for the same timepoints.

*CONFIDENTIAL*

Study Drug: DS-6157a

Sponsor/Innovations Study Numbers: DS6157-A-U101/GI 289

Final Protocol: 17 August 2021 Version 6.0

## 7.2 Screening

At enrollment, each potential research patient will provide written informed consent  $\leq 28$  days prior to initiation of treatment and prior to starting any study-specific procedures. Upon signature of the ICF, patients will be assigned a unique patient number as enrollment (screening) occurs.

The study will allow re-screening for any patient who failed to meet eligibility criteria upon initial screening. The failed screening test(s) and the other screening results that are out of window relative to the start of the study treatment, and any other protocol-specified screening tests per the Medical Monitor's guidance, will be re-tested during re-screening. The initial screening information and the reason why the patient was ineligible for the initial evaluation will be recorded in the Screening Log.

The screening assessments described in the [Assessment Schedule](#) will be collected, reviewed, and determined whether acceptable by the site Principal Investigator or designee after obtaining informed consent prior to the initiation of treatment.

The following screening parameters should be recorded  $\leq 7$  days prior to initiation of treatment:

- Medical history and demographics
- Cancer history and prior cancer therapies
- Smoking history
- Physical examination (including height and weight) and skin assessments
- ECOG performance status
- Vital signs (blood pressure, SpO2, body temperature, and pulse rate)
- Triplicate ECGs
- Hematology (red blood cell [RBC] count, hemoglobin [Hb], hematocrit, reticulocytes, total white blood cell [WBC] count, absolute neutrophil count [ANC], absolute lymphocyte count, 5-part % differential [neutrophils, lymphocytes, monocytes, basophils, eosinophils], and platelet count)
- Biochemistry (sodium, potassium, phosphate, chloride, creatinine, calcium, venous bicarbonate HCO3 or carbon dioxide (CO2), albumin, total protein, AST, ALT, alkaline phosphatase [ALP], bilirubin [total {required}/fractionated {direct/indirect} bilirubin, if available], lactate dehydrogenase, serum glucose, creatinine kinase [CK: if CK is elevated, then CK-MB, CK-MM, troponin I, and myoglobin should be reactively tested, with further follow-up as clinically warranted], blood urea nitrogen [BUN] or urea, and serum uric acid)
- Urinalysis (Dipstick); if abnormal and clinically significant, the Investigator must order a microscopic analysis of the urine sediment
- Screening pregnancy test (serum)
- Coagulation (PT, aPTT or PTT and INR)

If these assessments are performed within 72 hours of initiation of treatment, they do not need to be repeated on Cycle 1 Day 1 with the exception of the ECOG performance status, an

*CONFIDENTIAL*

abbreviated physical examination, vital signs, and triplicate ECGs. ECHO or MUGA, and tumor assessments (scans) should be performed  $\leq 28$  days prior to initiation of treatment. Tests for HIV infection, hepatitis B, and hepatitis C must be performed at screening. For subsequent cycles, all Day 1 assessments will have a 48-hour window except for ECHO/MUGA, which will have a 3-day window at Cycle 2 and a 7-day window for subsequent cycles.

Relevant medical history and concomitant medications present at study entry and/or during screening that are relevant to the patient's safety during the study as judged by the Investigator will be recorded in the electronic case report form (eCRF) (see Section 5.3 for details on concomitant medications).

### 7.2.1 Screen Failures and Rescreening

Screen failures are defined as patients who signed the informed consent form to participate in the clinical study but are not subsequently entered in the study. Individuals who do not meet the criteria for participation in this study (screen failure) may be rescreened. Rescreened patients should be assigned a new patient number that is different from the initial screening. Rescreening of a patient should be documented by recording the previous patient number on the eCRF so that its effect on study results, if any, can be assessed.

### 7.2.2 Tumor Imaging During Screening

Baseline tumor assessments must be performed within 28 days before first drug administration. Tumor responses must be assessed according to RECIST Version 1.1 (see [Appendix B](#)) and must include computed tomography (CT) scans or magnetic resonance imaging (MRI) of **the chest and abdominopelvic cavity** and, if clinically indicated, imaging of any other known or suspected sites of disease (e.g., brain) using an appropriate method (CT scan or MRI). If there is a history of CNS metastasis, a CT scan of the head or MRI of the brain must be performed. The same radiographic procedure must be used throughout the study. In case of suspected (but not otherwise confirmed) bone metastasis at screening or in subsequent cycles, tumor assessment must include a bone scan. Correlative imaging must then be repeated at each tumor assessment. Assessments will be performed by the Investigator.

Additionally, all images including CT and MRI may be submitted to a central imaging CRO for independent retrospective review.

### 7.3 Tumor Assessments During Study Treatment

Patient will remain on treatment as long as, in the opinion of the Investigator, they are deriving benefit and the criteria for withdrawal listed in Section 3.3 are not met. Please refer to the [Assessment Schedule](#) for detailed outlines of each visit during the treatment period for each part of the study.

Response will be assessed by CT scans or MRI of **the abdominopelvic cavity** (and chest ONLY if the screening imaging documented sites of disease in the chest) at 6-week intervals ( $\pm 7$  days) during the first 36 weeks and every 9 weeks ( $\pm 7$  days) thereafter, taking as reference the first dose date for non-randomized patients and the randomization date for randomized patients. Then, patients will be assessed at the EOT visit by CT scans or MRI of **the chest and**

*CONFIDENTIAL*

**abdominopelvic cavity**, and at the discretion of the Investigator. Patients will continue treatment with DS-6157a, until progression of disease (PD) according to RECIST Version 1.1 as assessed by the Investigator, initiation of new anti-cancer treatment, unacceptable toxicity, death, lost to follow up, or withdrawal of consent. However, patients may be treated beyond initial radiological progression (according to RECIST Version 1.1) on a case-by-case basis (with agreement from the Medical Monitor), if the Investigator feels that it is in the patient's best interest, the patient re-consents to continue receiving study treatment in a separate consent form, and as long as the patient is deriving benefit from the treatment, and no other criterion listed in Section 3.3 is fulfilled.

The assessments to be performed at this time are specified in [Appendix B](#) and will occur regardless of dose interruptions/delays. Please refer to Section 9 for further instructions on evaluating response (e.g., PD, SD).

The following assessments will be performed if abnormal at baseline or if clinically indicated:

- CT scan or MRI of the chest, abdomen, and pelvis/lower abdomen
- CT scan of the head/MRI of the brain if history of CNS metastasis
- Bone scan in case of suspected (but not confirmed) bone metastasis

Additionally, all images including CT and MRI may be submitted to a central imaging vendor for independent retrospective review.

### **7.3.1 Tumor Imaging by RECIST Version 1.1**

For RECIST Version 1.1 ([Appendix B](#)), the overall responses will be categorized as Complete Response (CR), Partial Response (PR), Stable Disease (SD), Progressive Disease (PD), or Not Evaluable (NE). For patients who experience an objective response of CR or PR, responses will be considered unconfirmed until the response has been documented by a subsequent confirmatory scan obtained no less than 4 weeks after the initial scan demonstrating an objective response.

## **7.4 Follow-up Periods and Study Completion**

### **7.4.1 End-of-Treatment Visit**

The end-of-treatment (EOT) visit will be performed after the Investigator decides with the patient to permanently discontinue the study treatment for any reason, as soon as possible but within 30 days of the last dose of treatment or before the patient starts another therapy, whichever occurs sooner.

The assessments of the EOT visit will then be performed instead of the next planned visit. If the patient discontinues treatment without having PD, the patient will be followed until the start of the next anti-cancer therapy, PD, death, lost to follow-up, withdrawn consent, or end of study, whichever occurs sooner.

*CONFIDENTIAL*

#### 7.4.2 30-day Safety Follow-up

All patients will be followed for at least 30 days after the last dose of study treatment during the off-treatment period until all treatment-related toxicity resolves, or before the start of another anti-cancer treatment. Any concomitant medications and procedures received up to 30 days after the last dose of study treatment must be recorded.

During this period, SAEs and AESIs occurring during the study that are considered to be related to study treatment or procedures will be followed for at least 30 days after the patient's last dose of DS-6157a. All new AEs occurring during this period must be reported and followed, unless, in the opinion of the Investigator, they are not likely to improve because of the underlying disease (see Section 3.3). In these cases, the Investigator must record his or her reasoning for this decision in the patient's medical records and indicate on the AE pages that the outcome is not resolved on the eCRF.

#### 7.4.3 Long-term Follow-up

Patients who did not experience progressive disease or death during the 30-day safety follow-up will be followed until the start of a new anti-cancer treatment, progressive disease, death, lost to follow up, withdrawal of consent, or at the discretion of the Investigator. Tumor assessment will be performed per RECIST v1.1 at the same frequency specified in Section 7.3 (i.e., every 6 weeks [ $\pm 7$  days] for the first 36 weeks and, every 9 weeks [ $\pm 7$  days] thereafter). If a new anticancer therapy is planned to start before the next planned tumor assessment, the tumor assessment may be performed just before starting the new therapy.

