- q 30-day safety follow-up will be performed for at least 30 days after the last study drug administration or before starting new anti-cancer treatment, whichever comes first, as described in Section 7.4.2. If the day of treatment discontinuation is over 30 days from last study drug administration, this follow up visit is not needed.
- r Patients who did not experience progressive disease or death during the 30-day safety follow-up will be followed until the start of a new anti-cancer treatment, progressive disease, death, lost to follow up, withdrawal of consent from any further participation, or at the discretion of the Investigator. Tumor assessment per RECIST v1.1 will be performed at the same frequency as for patients receiving treatment depending on when the discontinuation occurs (i.e., every 6 weeks [ $\pm 7$  days] for the first 36 weeks and, every 9 weeks [ $\pm 7$  days] thereafter). If a new anticancer therapy is planned to start before the next planned tumor assessment, the tumor assessment may be performed just before starting the new therapy.
- s If patient provides consent, samples should be collected prior to study drug infusion. Starting at Cycle 5, Day 1, every 4 cycles thereafter (Cycle 9, Cycle 13, etc.), and at the EOT visit. For patients with suspected or confirmed COVID-19 infections, follow the dose modifications in [Appendix H](#).
- t A washout period of no less than 14 days is required before restarting DS-6157.

*CONFIDENTIAL*

Study Drug: DS-6157a

Sponsor/Innovations Study Numbers: DS6157-A-U101/GI 289

Final Protocol: 17 August 2021 Version 6.0

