### **3.3 Discontinuation from Study Treatment**

Patients may be withdrawn from study treatment for any of the following reasons:

- Disease progression (PD) based on RECIST Version 1.1 criteria, where the patient is no longer receiving benefit in the opinion of the treating Investigator.
  - However, patients who are receiving benefit in the opinion of the treating Investigator may be allowed to stay on study on a case-by-case basis with agreement from the Medical Monitor and if the patient re-consents to continue receiving the study drug and meet the criteria listed in Section 5.2.

Clinical progression (definitive clinical signs of PD), but a recent radiographic assessment did not meet the criteria for PD according to RECIST Version 1.1

- Adverse event
- Death
- Pregnancy
- Withdrawal of consent by patient
- Lost to follow-up
- Physician decision
- Study terminated by Sponsor
- Other

After discontinuation from protocol treatment, patients must be followed for AEs for at least 30 days after their last dose of study drug. All new AEs occurring during this period must be reported and followed until resolution, unless, in the opinion of the Investigator, these values are

*CONFIDENTIAL*

not likely to improve because of the underlying disease. In this case, the Investigator must record his or her reasoning for this decision in the patient's medical records and indicate on the AE pages that the outcome is not resolved on the electronic case report form (eCRF).

All patients who have Grade 3 or 4 laboratory abnormalities (per National Cancer Institute Common Terminology Criteria for Adverse Events [NCI CTCAE Version 5.0]) at the time of discontinuation must be followed until the laboratory values have returned to Grade 1 or 2, unless it is, in the opinion of the Investigator, not likely that these values are to improve. In this case, the Investigator must record his or her reasoning for making this decision in the patient's medical records and indicate on the AE pages that the outcome is not resolved on the eCRF.

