### 10.5.2 Efficacy Analysis

Efficacy analyses will be based on FAS. If multiple doses or regimens were selected for Dose Expansion (Part 2) and not all randomized patients receive at least one dose of DS-6157a dose/regimen as randomized, sensitivity analyses will be performed for the Safety Analysis Set.

Efficacy variables will include BOR, ORR, DCR, CBR, DoR, TTR, and PFS using RECIST Version 1.1. In this study, best response determination using RECIST Version 1.1 requires confirmation of CR or PR.

A brief description of each endpoint is provided below.

- The BOR will be determined using tumor assessments performed before the start of any follow-up anticancer therapies (i.e. anticancer drug, radiotherapy, or surgery).
  - CR = at least two determinations of CR at least 4 weeks apart before progression.
  - PR = at least two determinations of PR or better at least 4 weeks apart before progression (and not qualifying for a CR).
  - SD = at least one SD assessment (or better) >6 weeks after randomization/starting treatment and before progression (and not qualifying for CR or PR).
  - PD = progression  $\leq$ 12 weeks from randomization/start of study treatment (and not qualifying for CR, PR, or SD).
  - NE = all other cases
- ORR is defined as the proportion of patients with BOR of CR or PR.
- DCR is defined as the proportion of patients with BOR of CR, PR, or SD.
- CBR is defined as the proportion of patients with BOR of CR or PR, or patients with SD lasting at least 180 days.
- DoR is defined as the duration from the first documented response to the date of progression or death due to any cause. In case a patient does not have progression or death, DoR is censored at the date of last adequate tumor assessment (defined as an assessment of CR, PR, or SD). DoR analysis will include only responders.
- TTR is defined as the time from randomization/start of study treatment to the date of first documented response. TTR analysis will include only responders.
- PFS is defined as the time from randomization/start of study treatment to the date of event defined as the first documented radiological progression or death due to any cause. If a patient has not had an event, PFS is censored at the date of last adequate tumor assessment.

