**Special notes on response evaluation**

*Missing assessments and non-evaluable designation:* When no imaging/measurement is done at all at a particular time point, the patient is not evaluable (NE) at that time point. If only a subset of lesion measurements are made at an assessment, usually the case is also considered NE at that time point, unless a convincing argument can be made that the contribution of the individual

CONFIDENTIAL

missing lesion(s) would not change the assigned time point response. This would be most likely to happen in the case of PD.

*Symptomatic progression:* Patients with a global deterioration of health status requiring discontinuation of treatment without objective evidence of PD at that time should be reported as “symptomatic deterioration.” Every effort should be made to document objective progression even after discontinuation of treatment. Symptomatic deterioration is not a descriptor of an objective response: it is a reason for stopping study treatment.

*Confirmation of response:* Confirmation of response (by repeat scans after 4 weeks or as specified in the protocol) is required.

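### Sections 7.4.1 and 7.4.3 disagree on when tumor follow-up may end after stopping treatment without progression, and the investigator-discretion exit can bias the descriptive PFS and DoR estimates upward

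*Combined protocol and SAP*

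**What the plan says.** **Follow-up after stopping without PD.** Section 7.4.1 states that "the patient will be followed until the start of the next anti-cancer therapy, PD, death, lost to follow-up, withdrawn consent, or end of study", whichever comes first. Section 7.4.3 addresses patients with no progression or death by the end of the 30-day safety follow-up and ends its list with "lost to follow up, withdrawal of consent, or at the discretion of the Investigator". Assessment Schedule footnote r ends with "withdrawal of consent from any further participation, or at the discretion of the Investigator". Neither 7.4.3 nor footnote r says when the discretion may be used.

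**Stopping treatment.** Section 3.3 lists among the reasons "Clinical progression (definitive clinical signs of PD), but a recent radiographic assessment did not meet the criteria for PD".

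**Scan at the end of treatment.** Section 7.3, footnote g and the EOT column of the Assessment Schedule provide for CT or MRI at the EOT visit. Section 7.4.1 places that visit within 30 days of the last dose, or before another therapy if sooner. Section 7.4.4 asks every patient who discontinues to have the EOT assessments.

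**Endpoints.** Section 10.5.2 defines the PFS event as "the first documented radiological progression or death due to any cause". Without an event, PFS and DoR are censored at the last adequate tumor assessment. Table 1 lists both among the seven efficacy endpoints for the primary objective of Dose Expansion.

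**Symptomatic deterioration.** Appendix B says: "Every effort should be made to document objective progression even after discontinuation of treatment".

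**The concern.** A site can comply with 7.4.3 and depart from 7.4.1 for the same patient. The patients for whom an investigator is most likely to end follow-up early include those who look clinically worse. Their progression is not a PFS event until a scan shows it or they die. If scanning stops first, they are censored at a scan still read as CR, PR or SD.

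Kaplan-Meier estimation assumes that a censored patient has the same outlook as those still followed. Here the outlook would be worse, so the curve would sit too high. The expansion cohorts have up to about 30 patients each and no dose comparison is planned, so no comparator estimate offsets such a bias. Appendix B aims at the opposite practice, and the discretion clause undercuts it.

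**Working it through.** **Step 1. The texts side by side.** All four end follow-up, or scanning in the case of footnote g, at new anti-cancer therapy, PD, death and loss to follow-up. They differ as follows.

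| Text | Investigator discretion | Consent stop | Other |
|---|---|---|---|
| 7.4.1 | not listed | consent withdrawn | end of study |
| 7.4.3 | listed, no criterion | consent withdrawn | none |
| Footnote r | listed, no criterion | withdrawn from all further participation | none |
| Footnote g | phrase present, joined by *and* | withdrawn from all further participation | unacceptable toxicity |

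Footnote g can be read as allowing extra scans, as the parallel sentence in 7.3 does, or as a further stop. It needs to be made clear either way.

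**Step 2. The route to censoring.** Four things must happen:
1. Treatment stops for clinical progression without RECIST PD.
2. The EOT scan is missed or does not show PD.
3. No new anti-cancer therapy starts. If it does, 7.4.1 also ends follow-up.
4. The investigator ends follow-up under 7.4.3 before a later scan or death.

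**Step 3. Is there a figure to reproduce?** The protocol states no assumed PFS or DoR, so no. The only efficacy sample-size figures are the Clopper-Pearson limits in Table 3. They reproduce: for 11/30 = 36.7%, the 90% interval is 22.1% to 53.3% and the 95% interval 19.9% to 56.1%. They concern ORR and do not depend on this point.

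**Step 4. Upper-bound illustration.** Assume exponential PFS with median m, and a share f of patients censored just before their event. The estimated hazard falls by the factor (1 − f), so the median becomes m/(1 − f):
- f = 10%: 1/0.90 = 1.11, or +11%
- f = 20%: 1/0.80 = 1.25, or +25%
- f = 30%: 1/0.70 = 1.43, or +43%

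The next table uses the protocol's scan schedule (every 6 weeks to week 36, then every 9) and 200,000 simulated patients. No EOT scan, new therapy or deaths are modelled, and f and the true medians are assumed.

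| True median | Measure | f = 0 | 10% | 20% | 30% |
|---|---|---|---|---|---|
| 3 months | 24-week PFS | 27.9% | 31.2% | 34.9% | 39.2% |
| | KM median (weeks) | 18 | 18 | 18 | 18 |
| 6 months | 24-week PFS | 52.8% | 56.0% | 59.6% | 63.3% |
| | KM median (weeks) | 30 | 30 | 36 | 45 |
| 9 months | 24-week PFS | 65.3% | 68.1% | 70.8% | 73.9% |
| | KM median (weeks) | 45 | 45 | 54 | 63 |

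24-week PFS rises in every case. The median can move only in steps of the scan schedule and sometimes does not move.

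**Step 5. Take out the new-therapy route.** With a 6-month true median, suppose half of those stopped start new therapy. At f = 10%, 20% and 30%, 24-week PFS is 54.4%, 56.0% and 57.7% under 7.4.1, and 56.1%, 59.4% and 63.2% under 7.4.3. The part due to the clause is the difference: 1.7, 3.4 and 5.5 percentage points. The bias already present under 7.4.1, measured from 52.8%, is 1.6, 3.2 and 4.9 points.

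**Step 6. Take out the EOT scan as well.** Assume 20% stop for clinical progression, the EOT scan shows PD in half of them (10% remain), and half of the remainder start new therapy. The censored share is then 10% under 7.4.3 and 5% under 7.4.1. The ratio of medians is 0.95/0.90 = 1.056, about +6% rather than +25%. At 20% stopped, the clause could account for anything from 0 (the EOT scan catches everyone, or all the rest start new therapy) to 25% (neither happens).

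**The case against.** The strongest reply is that the protocol already schedules a scan at the decisive moment. The EOT scan comes before 7.4.3 applies, so the discretion clause reaches only patients whose EOT scan was missed or negative. Many of those will go on to another therapy, which ends follow-up whichever section is used. Appendix B asks sites to keep looking for objective progression. No hypothesis test or dose comparison is planned, and the efficacy conclusion in Section 10.3 rests on ORR. Sections 10.2 and 10.6 leave further methods to a SAP whose text is not in the document reviewed, so one cannot say that no sensitivity analysis will be done.

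Most of this stands, and it limits the point. It does not remove it: EOT scans can be missed or negative, Appendix B is best-effort wording, and no text says that 7.4.1 prevails over 7.4.3.

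Three stronger readings are tempting and are not supported:
- **That the clause inflates PFS by 11% to 43%.** Those figures charge every lost patient to investigator discretion and ignore the EOT scan and new therapy.
- **That the consent wording is a second contradiction.** Sections 7.4.1 and 7.4.3 concern patients already off treatment, so withdrawn consent there naturally means consent to follow-up. The wording merely differs from footnotes g and r.
- **That 10.5.2 expressly limits DoR to radiological progression.** Only the PFS definition uses that word. For DoR it follows from the statement that the efficacy variables use RECIST 1.1.

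**Conclusion.** The inconsistency is in current operative text. Applied as written, 7.4.3 and footnote r permit censoring related to imminent progression, and the direction of any resulting bias in PFS and DoR is upward. DoR was not simulated; the direction follows from its sharing the PFS censoring rule.

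The size cannot be stated. The documents give neither the share of patients who stop for clinical progression, nor the yield of the EOT scan, nor how often new therapy follows. Under the assumptions in Step 6 the clause adds about 6% to the median, and the simulated figures without those two corrections are upper bounds. A reader might infer that the trial's efficacy conclusion is compromised. It is not: ORR does not use this censoring rule, the sample size rests on ORR, and PFS and DoR are descriptive. This is a cheap improvement, not a design flaw.

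**What to change.** 1. Delete investigator discretion as a reason to end tumor follow-up in Section 7.4.3 and footnote r.
2. Reconcile footnote g with 7.4.1. Its stop list contains unacceptable toxicity, which 7.4.1 does not, and its discretion phrase should say plainly whether it permits extra scans or ends scanning.
3. Use the 7.4.1 list in all of these places.
4. As a clarification, use footnote r's consent wording in 7.4.1 and 7.4.3, so that tumor follow-up ends only when the patient withdraws from all further participation.

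The cost is a wording change in four places and a few more of the scans already scheduled in 7.4.3. Patients keep the right to withdraw completely. The change does not touch censoring at new anti-cancer therapy. If the SAP does not already cover that, a sensitivity analysis counting clinical progression and start of new therapy as events would show how much it matters.
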